**7.1.2 Arm LMP-TC**

End of therapy is Day 42 of Course LMP-TC1 for patients with a CR or PD after this course and for patients with PR or SD after this course who do not have a suitable T-cell product available for Course LMP-TC2.

End of therapy is Day 42 of Course LMP-TC2 for all other patients.

**7.1.3 Observations During Follow-up**

Observations During Follow-up After Completion of Therapy	1 Months	2 Months	3 Months	6 Months	9 Months	12 Months						
History and Physical exam	X	X	X	X	X	X						
Performance status	X	X	X	X	X	X						
Documentation of immunosuppressive medication	X	X	X	X	X	X						
If applicable tacrolimus, sirolimus, cyclosporine level	X	X	X	X	X	X						
CBC, diff	X	X	X	X	X	X						
Electrolytes, BUN, creatinine	X	X	X	X	X	X						
AST, ALT, total and direct bilirubin, albumin, total protein, LDH	X	X	X	X	X	X						
CT* of involved areas	As needed for clinical symptoms											
Endoscopy of involved areas	As needed for clinical symptoms											
Specimens for Submission to BCM												
See Section 15 for Details												
EBV PCR (Required for all patients): 5 mL whole Blood in EDTA (purple top)	X	X	X	X	X	X						
Correlative biology studies (for patients consenting for the optional studies)	Arm LMP-TC follow-up time points are calculated from Day 0 of LMP-TC1 regardless of LMP-TC2 participation. See Section 15 For a detailed guide to the follow-up sampling time points.											

\* And/or MRI, PET. The same method of assessment and the same technique should be used at baseline and during follow-up. See [Section 10.2](#).

See COG Late Effects Guidelines for recommended post treatment follow-up:  
<http://www.survivorshipguidelines.org/>

**Note:** Follow-up data are expected to be submitted per the Case Report Forms (CRFs) schedule.

## 7.2 Biology Research Studies

This section is provided as a brief overview of required and optional biology studies. See [Section 15](#) for a detailed guide for time points, specimen requirements and shipping instructions.

Study		Before or During Induction	During Course RTX2	After Course RTX2	During Course LMP-TC1	After Course LMP-TC1	In Case of CRS	In Case of Allograft Rejection or Failure
Required	EBV PCR	X	X	X	X	X		
Optional	General immune reconstitution		X	X	X	X	X	
	Persistence of LMP-specific T cells		X	X	X	X		X*
	Immunity to EBV		X	X	X	X		

\*Submission only in case of suspected allograft rejection or failure during Course LMP-TC1 or LMP-TC2.  
Obtain specimen prior to increasing immunosuppression or commencing steroid therapy.

## 8.0 CRITERIA FOR REMOVAL FROM PROTOCOL THERAPY AND OFF STUDY CRITERIA

### 8.1 Criteria for Removal from Protocol Therapy

- a) Repeat eligibility studies (if required) are outside the parameters required for eligibility (see [Section 3.2.](#)).
- b) Pregnancy.
- c) Evidence of Hepatitis B or C infection during any course of treatment with rituximab (or biosimilar).
- d) Unacceptable toxicity due to protocol therapy (See [Section 5.2](#) and [Section 5.3](#)).
- e) Progressive disease after or during Course RTX2, Course LMP-TC1, Course LMP-TC2.
- f) Assigned to Arm LMP-TC without an available matched LMP-specific T-cell product.
- g) Assigned to Arm LMP-TC without HLA typing available by the Day 22 post-induction Callback.
- h) Refusal of further protocol therapy by patient/parent/guardian.
- i) Physician determines it is in the patient's best interest.
- j) Development of a second malignancy.
- k) Completion of planned protocol therapy.
- l) Inability to attain and maintain therapeutic immunosuppressive drug levels on the LMP TC arm

Patients who are off protocol therapy are to be followed until they meet the criteria for Off Study (see below). Follow-up data will be required unless patient is taken off study.

### 8.2 Off Study Criteria

- a) Death.
- b) Lost to follow-up.
- c) Patient enrollment onto another COG study with tumor therapeutic intent (e.g., at recurrence).
- d) Withdrawal of consent for any further data submission.
- e) The fifth anniversary of the date the patient was enrolled on this study.
- f) No treatment received.

## 9.0 STATISTICAL CONSIDERATIONS

### 9.1 Sample Size and Study Duration

Review of patient accrual onto recent phase 2 PTLD studies and personal communication from Canadian investigators indicates the following entry rates can be expected:

Disease Group	Patients/Year
Post-Transplant Lymphoproliferative Disorder (PTLD)	19

The study will likely require 3.1 to 4.9 years to enroll sufficient patients to evaluate LMP-specific T cells in the stated disease group. A maximum of 90 eligible patients is anticipated to obtain at least 30 patients evaluable for the primary endpoint.

Patients in Cohort A (newly diagnosed) are assigned to Arm LMP-TC only if they fail to achieve a CR after Course RTX1, while patients in Cohorts B (relapsed) and C (refractory) are automatically assigned to Arm LMP-TC. To avoid going too far past the targeted sample size of 30 patients evaluable for the primary aim (i.e., assigned to Arm LMP-TC) while avoiding the need to repeatedly open and close the trial to enrollments, we will closely monitor enrollments when the number of patients assigned to Arm LMP-TC approaches 30. The number of available enrollments will be limited to the smallest number such that there is a 90% chance of reaching 30 patients assigned to Arm LMP-TC assuming each patient in Cohort A has a 40% chance of being assigned to Arm LMP-TC and all patients in Cohort B and C will be assigned to Arm LMP-TC. If at any time the number of patients enrolled in Cohort A but not having reached Callback equals or exceeds this threshold, the study will be closed to accrual until all patients currently enrolled have either been assigned to either Arm RTX or Arm LMP-TC or have been removed from protocol therapy. If after that there are fewer than 30 patients assigned to Arm LMP-TC, the study will be re-opened with the number of available slots as in the table below.

The table below displays the maximum number patients that will be allowed to be enroll, the probability of reaching 30 patients on Arm LMP-TC if there are exactly that many patients in Cohort A pre-Callback, and the probability of exceeding 36 patients on Arm LMP-TC if there are exactly that many patients in Cohort A pre-Callback.

Current Cohort A patients assigned to Arm LMP-TC plus all patients in Cohorts B and C	Maximum number of Cohort A patients pre-Callback	Probability of reaching 30 patients on Arm LMP-TC	Probability of exceeding 36 patients on Arm LMP-TC
21	30	90.6%	9.7%
22	27	90.5%	7.4%
23	24	90.4%	5.3%
24	21	90.4%	3.5%
25	18	90.6%	2.0%
26	15	90.9%	0.9%
27	12	91.7%	0.3%
28	9	92.9%	<0.1%
29	5	92.2%	—

## 9.2 Study Design

The primary endpoint of the study ([Aim 1.1.1](#)) is the percentage of patients assigned to Arm LMP-TC who had a suitable LMP-specific T-cell product, were treated within two weeks of the expected start date (Callback for Cohorts A and B, study enrollment for Cohort C), and received both weekly doses in a cooperative multi-institutional setting. All 3 Cohorts will be analyzed together for the primary aim.

The main secondary endpoint of the study ([Aim 1.2.1](#)) is the percentage of all eligible patients who had a suitable LMP-specific T-cell product derived from a Third Party LMP-specific T-cell bank available in a cooperative multi-institutional setting. Additional secondary endpoints ([Aims 1.2.2-1.2.8](#)) will be the estimation of progression-free survival (PFS), event-free survival (EFS), overall survival (OS), response rate (RR), and toxicity rates in the study population.

At least thirty (30) patients evaluable for the primary endpoint will be enrolled, with a futility analysis after 15 patients. The study will be considered successful if 23/30 evaluable patients in the trial are matched, are treated within two weeks of the expected start date, and receive both weekly doses of LMP-specific T cells. If exactly 23/30 successes occurred, the one-sided exact binomial 95% confidence interval (adjusted for the interim analysis by the method of Jung and Kim)[37](#) would be  $p > 60.7\%$ , which would exclude the possibility that the true success rate is as low as 60%. If the true success rate in the study population is 80%, then the proposed sample size of 30 will give 75.3% power to get at least 23/30 successes. If the true success rate in the study population is 60%, then there is a 4.2% chance of getting at least 23/30 successes.

Since evalability for the primary endpoint depends on the response to the initial treatment with rituximab for patients in Cohort A (newly diagnosed patients), it is possible that more than 30 patients will be evaluable for the primary endpoint. In that case, the trial will be considered successful if the one-sided exact binomial 95% confidence interval excludes the possibility that the true success rate is as low as 60%. The required number of successes and power under various scenarios is displayed below.

Number of evaluable patients	Number of successes needed	Power (80% true rate)	Power (60% true rate)
30	23	75.3%	4.2%
31	24	72.4%	3.2%
32	25	69.3%	2.4%
33	25	78.7%	4.2%
34	26	76.2%	3.3%
35	27	73.5%	2.5%
36	27	81.4%	4.2%

## 9.3 Methods of Analysis

For the primary endpoint, the point estimate of the proportion successfully matched and treated (among all 3 Cohorts combined) will be the uniformly minimum variance unbiased estimator, and an exact one-sided binomial 95% confidence interval (adjusted for the interim analysis by the method of Jung and Kim)[37](#) will be used to get a lower bound for the actual rate of successful treatments as defined in the primary objective.

For the secondary endpoints:

- The proportion of eligible patients who are successfully matched will be assessed using the uniformly minimum variance unbiased estimator for the proportion and an exact one-sided binomial 95% confidence interval (adjusted for the interim analysis by the method of Jung and Kim) to get a lower bound for the actual rate.
- PFS (defined as time to first occurrence of progression or death (events) or loss to follow-up or survival to analysis date (non-events)), EFS (defined as time to first occurrence of relapse, second/secondary malignant neoplasm (SMN), death (events) or loss to follow-up or survival to analysis date (non-events)), and OS (defined as time to death (event) or loss to follow-up or survival to analysis date (non-events)) will be assessed using Kaplan-Meier estimates, both for all patients combined and also separately in each Cohort. Aim 1.2.8 will be assessed using the Log-Rank test for EFS and OS and the exact conditional test of proportions (Fisher's Exact test) for RR, both for all patients combined and stratified by Cohort.
- Response rates will be assessed using exact two-sided binomial 95% confidence intervals to get estimates of the response rate. Aim 1.2.2 will be evaluated in Cohorts A and B only (combined and separately), with response classified by comparing disease evaluation at the Week 3 evaluation to the baseline of disease evaluation at study entry using the criteria in Section 10.2. Patients with CR will be considered responders. For Aim 1.2.5, response will be classified by comparing disease evaluation at the Week 6 of LMP-CT1 evaluation to the baseline of disease evaluation at the Week 3 evaluation using the criteria in Section 10.2, both in all Cohorts combined and in each Cohort separately. Patients with CR or PR will be considered responders.
- Toxicities will be described using descriptive statistics. Toxicity monitoring and analysis will be performed based on "as treated".

We will assess the proportion of successes for the primary aim on the first 15 patients assigned to Arm LMP-TC as an interim futility monitoring rule. If fewer than 10 of the first 15 patients are successes for the primary aim (matched and treated within the prescribed timeframe), the Study Committee will assess the reasons for failure and may choose to close the study if it is felt that the reasons are not correctable. If the true success rate is 60%, this rule will be invoked with probability 59.7%; if the true success rate is 80%, the rule will be invoked with probability 6.1%.

We will do real-time monitoring for progression rate at week 10 and for certain protocol-specific toxicities, namely: allograft failure, allograft rejection, cytokine release syndrome grade 3 or higher, and graft versus host disease (see [Appendix V](#)). The monitoring will be done using Bayesian rules with beta priors. The four parameters for each scenario are the two beta distribution parameters ( $\alpha, \beta$ ), the unacceptable probability rate for the event we are monitoring ( $p_0$ ), and the posterior probability that the actual rate exceeds  $p_0$  ( $P(p > p_0 | \text{Data})$ ), which is calculated using the standard Bayesian posterior probability formula

$$P(p > p_0 | \text{Data}) = \frac{\int_{p_0}^1 \binom{n}{x} p^x (1-p)^{n-x} \frac{\Gamma(\alpha + \beta)}{\Gamma(\alpha)\Gamma(\beta)} p^{\alpha-1} (1-p)^{\beta-1} dp}{\int_0^1 \binom{n}{x} q^x (1-q)^{n-x} \frac{\Gamma(\alpha + \beta)}{\Gamma(\alpha)\Gamma(\beta)} q^{\alpha-1} (1-q)^{\beta-1} dq},$$

where  $n$  is the number of observations and  $x$  is the number of events among those  $n$  observations.

We will suspend enrollment to the study if any patient suffers or is suspected to suffer allograft failure or allograft rejection to review the circumstances of the failure or rejection. A recommendation to re-open enrollment might be made if causes other than study therapy were thought to be the primary cause of failure or rejection.

For cytokine release syndrome and graft versus host disease, the analytic unit for monitoring for protocol-specific toxicities will be the patient-course. Each course where the patient receives the agent or where a protocol-specific toxicity event is observed will be considered in the analysis. We will assume a beta prior distribution with  $\alpha = 0.6$  and  $\beta = 1.4$  and an unacceptable toxicity rate of  $p_0 = 30\%$ . At least once per month, we will calculate the posterior probability (given the data) that the probability of protocol-specific toxicity exceeds the 30% threshold, *i.e.*,  $P(p > 0.3 | \text{Data})$ . If there is a posterior probability of 80% that the toxicity rate is at least 30%, then accrual will be suspended pending review by DSMC. Examples of situations in which this rule will indicate protocol-specific toxicities have been noted and are presented below:

Number of failures	Number of patient-cycles
2	3
3	6
4	8
5	11
6	14
7	17
8	20
9	23
10	26
11	29
12	32
13	35
14	38

Interim monitoring will also be performed to watch for a 20% progression rate at week 10 in newly-diagnosed patients and a 40% progression rate at week 10 for relapsed and refractory patients. For newly-diagnosed patients, the beta parameters will be  $\alpha = 0.52$  and  $\beta = 2.08$ ; and for relapsed and refractory patients the beta parameters will be  $\alpha = 1.04$  and  $\beta = 1.56$ ; if there is a posterior probability of 80% that the progression rate at week 10 is at least 20% for newly-diagnosed patients or 40% for relapsed/refractory patients, then accrual for the respective cohort or cohorts will be suspended pending review by the DSMC. The stopping rule will be triggered as described in the following table:

Number of failures	Number of newly-diagnosed patients	Number of relapsed/refractory patients
2	4	2
3	8	4
4	12	6
5	16	8

6	20	11
7	24	13
8	29	15
9	33	17
10	38	19

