### 1.2 Secondary Aims

- 1.2.1 To determine the percentage of eligible patients for whom a suitable LMP-specific T-cell product derived from a Third Party LMP-specific T-cell bank is available.
- 1.2.2 To estimate the response rate (RR) to three doses of RTX as single agent in children and young adults with newly diagnosed or relapsed EBV-Positive CD20-Positive PTLD after solid organ transplantation (SOT).
- 1.2.3 To estimate the 2-year event-free survival (EFS) of children and young adults with newly diagnosed, refractory or relapsed EBV-Positive CD20-Positive PTLD after SOT treated with RTX and/or LMP-specific T cells.
- 1.2.4 To estimate overall survival (OS) of children and young adults with newly diagnosed, refractory or relapsed EBV-Positive CD20-Positive PTLD after SOT treated with RTX and/or LMP-specific T cells.
- 1.2.5 To estimate the RR to LMP-specific T cells of newly diagnosed (without complete response to Course RTX1), refractory, and relapsed children and young adults with EBV-Positive CD20-Positive PTLD.
- 1.2.6 To estimate progression-free survival (PFS) of children and young adults with newly diagnosed, refractory or relapsed EBV-Positive CD20-Positive PTLD after SOT treated with RTX and/or LMP-specific T cells.
- 1.2.7 To describe the toxicity of Third Party LMP-specific T cells in children and young adults with newly diagnosed, refractory or relapsed EBV-Positive CD20-Positive PTLD after SOT treated with RTX and/or LMP-specific T cells.
- 1.2.8 To validate that absence of EBV viremia correlates with RR, EFS and OS.

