3.2.2.2.1 CD20 positive

3.2.2.2.2 EBV positive by EBER in situ hybridization (preferred) and/or LMP immunoperoxidase staining.

3.2.2.3 There must be evaluable disease at study entry either by imaging or by serial endoscopic biopsies.

Note: as indicated in [Section 10.2.5.1](#) a measurable node must have an LDi (longest diameter) greater than 1.5 cm. A measurable extranodal lesion should have an LDi greater than 1.0 cm. All tumor measurements must be recorded in millimeters (or decimal fractions of centimeters).

3.2.2.4 Patients must be considered medically refractory to decreased immunosuppression (50% or greater reduction) for at least 1 week or there must be documentation in the medical chart that decreased immunosuppression would be associated with an unacceptable risk of rejection.

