**and/or**

##### MTOR Inhibitors

Sirolimus (dose range per institutional guidelines) to achieve minimum level of 4 ng/ml

or

Everolimus (dose range per institutional guidelines) to achieve minimum level of 3 ng/ml

*For patients on combination therapy, the minimum level needs to be maintained at least for the calcineurin inhibitors.*

**Close monitoring of immunosuppression as per institutional guidelines is required. Calcineurin inhibitor and/or MTOR inhibitor levels are required weekly. If levels are subtherapeutic, adjust dose(s) as per institutional guidelines and repeat levels approximately every 48-72 hours until the therapeutic range has been reached. [See Section 4.4.5](#)**

**Course LMP-TC1 (42 days):** Patients with a suitable LMP-specific T-cell product will receive the closest HLA matched product at a dose of  $2 \times 10^7$  cells/m^2/dose on Days 0 and 7 followed by a response evaluation completed during Days 36-41 and submitted via the Callback form by Day 42 (see [Section 3.1.7](#)). Patients with CR at the end of LMP-TC1 have completed protocol therapy. Patients with PD at the end of LMP-TC1 go off protocol therapy with a recommendation to receive further chemotherapy per institutional guidelines.

**Course LMP-TC2 (42 days):** Patients with PR or SD after LMP-TC1 and with a suitable product available will be assigned to Course LMP-TC2 to receive two additional doses of LMP-specific T cells.

1. If the patient had a PR and a sufficient number of vials of cells remain, the LMP-TC2 doses should come from the same product used in LMP-TC1.
2. If the patient had SD and/or insufficient cells remain in the original product, the LMP-TC2 doses may be selected from another product if an additional suitably matched product is available.

Except for the Induction course (RTX1) up to the start of Arm LMP-TC or Arm RTX, all patients with progressive disease during protocol therapy will be taken off protocol therapy to receive chemotherapy according to institutional guidelines.

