#### 4.3.4 Post RTX2 Response Assessment

Evaluation by CT with contrast should be completed during Week 3 of Course RTX2. See [Section 10.2](#) for specific instances in which MRI or PET are recommended in addition to or as an alternative modality to CT.

Following completion of RTX2, patients have completed protocol therapy.

For patients who develop PD, chemotherapy as per institutional guidelines is strongly recommended.

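### Section 9.3 leaves progression off the EFS event list and relapse is undefined, so on a literal reading 2-year EFS can exceed PFS in the same patients

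*Combined protocol and SAP*

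**What the plan says.** One sentence in Section 9.3 defines all three time-to-event endpoints. For EFS it reads "EFS (defined as time to first occurrence of relapse, second/secondary malignant neoplasm (SMN), death (events"; for PFS it reads "PFS (defined as time to first occurrence of progression or death (events". Non-events are the same for both: loss to follow-up, or being alive when the analysis is done.

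Section 10.2.9 repeats the PFS definition and starts the clock at the beginning of treatment. EFS has no matching entry in Section 10 and is not defined anywhere else. Section 10.2.7 gives criteria for CR, unconfirmed CR, PR, SD and PD, and none for relapse.

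EFS is used twice. Aim 1.2.3 estimates it at 2 years. Aim 1.2.8 is "To validate that absence of EBV viremia correlates with RR, EFS and OS", and for this Section 9.3 says "Aim 1.2.8 will be assessed using the Log-Rank test for EFS and OS", with Fisher's exact test for RR. PFS (Aim 1.2.6) is estimated but is not part of Aim 1.2.8.

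Every patient starts with disease present: "There must be evaluable disease at study entry either by imaging or by serial endoscopic biopsies" (Section 3.2.2.3). Section 8.1(e) makes "Progressive disease after or during Course RTX2, Course LMP-TC1, Course LMP-TC2" a reason to stop protocol therapy, and Section 8.1 keeps such patients in follow-up until an off-study criterion in 8.2 is met.

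**The concern.** In this population a common form of failure is growth of disease that never cleared. PFS counts it at once. The EFS list, as written, does not name it. If an analyst programs Section 9.3 word for word and takes relapse in its ordinary sense of disease returning after CR, progression without prior CR is not an EFS event when it happens.

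Two secondary results would be affected. The 2-year EFS estimate, overall and by cohort, could come out above PFS in the same patients, although EFS would normally be expected to be the more inclusive endpoint. And the EFS log-rank comparison by EBV viremia would run on fewer events, missing the disease failures that the biomarker is meant to track.

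**Working it through.** The plan states no expected EFS or PFS, so there is no figure to reproduce. The check compares the definitions, follows a patient through them, and illustrates the possible size.

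**1. Event lists side by side (Section 9.3)**

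| First event | PFS | EFS as written |
|---|---|---|
| Progression, no prior CR | event | not listed |
| Failure after CR | event, if classed as PD | event (relapse) |
| SMN | not an event | event |
| Death | event | event |

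EFS can therefore be longer than PFS (first row) or shorter (third row). Section 9.4 uses the same evaluability rule for both, so the patient sets do not explain a difference.

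**2. What happens to a patient who progresses without CR**

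- Section 4.1.2.2 says that "Except for the Induction course (RTX1) up to the start of Arm LMP-TC or Arm RTX, all patients with progressive disease during protocol therapy" come off protocol therapy for chemotherapy.
- Progression is not itself an off-study criterion in 8.2, and the time limit there is the fifth anniversary of enrollment. Such a patient can be followed past 2 years.
- On the literal list the patient stays at risk until a later relapse, an SMN or death.
- Alternatively the patient is censored, for example under 8.2(c) on joining another COG study with therapeutic intent. The progression is uncounted in that case too.

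**3. Illustration from the protocol's own background (Section 2.4.2)**

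Inputs, German pediatric rituximab series: 14 patients in CR after three doses, with 1 relapse; 17 in PR, of whom 6 had progressive disease. Total 14 + 17 = 31. Table 1 gives 32 responders.

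- Literal list, if none of the six later had a listed event: 1/31 = 3.2% (1/32 = 3.1%).
- Progression counted: (1 + 6)/31 = 7/31 = 22.6% (7/32 = 21.9%).
- Gap: 6/31 = 19.4 points (6/32 = 18.75 points).
- Lower limit: 0, if relapse includes progression, or if all six later relapsed, died or had an SMN within the window.

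For a log-rank test in that subgroup, the literal list gives 1 to 7 events from these seven patients, against 7 with progression counted. Deaths or SMNs among the others would add equally to both.

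These are crude proportions. Deaths, SMNs and event times are not given. The 17 of 49 patients (35%) with SD or PD are left out because their later events are not reported.

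**4. Illustration from the week-10 progression rates in Section 9.3**

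The monitoring rules use 20% (newly diagnosed) and 40% (relapsed or refractory). These are monitoring thresholds, not forecasts. Assume that exactly these shares *p* progress without CR, that a share *d* of them die within 2 years, and that nothing else happens. Then PFS = 1 − *p* and literal EFS = 1 − *p* × *d*.

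| | PFS | Literal EFS, *d* = 20% | *d* = 50% | *d* = 80% |
|---|---|---|---|---|
| *p* = 20% | 80% | 96% | 90% | 84% |
| *p* = 40% | 60% | 92% | 80% | 68% |

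The values of *d* are assumptions; the documents give none.

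**5. What the RR test in Aim 1.2.8 recovers**

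Under 9.3 a responder is a CR at the Week 3 evaluation (Aim 1.2.2), or a CR or PR at Week 6 of LMP-TC1 (Aim 1.2.5). PD at either evaluation is therefore non-response. Progression after those evaluations in a patient never in CR is missed by both the RR test and literal EFS.

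**The case against.** The strongest reply is that relapse was simply meant to include progression, so nothing is biased. There is real support for this:

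- The protocol uses PD for failure after CR. Section 4.3.4, which concerns patients treated because they were in CR, says "For patients who develop PD, chemotherapy as per institutional guidelines is strongly recommended". Section 8.1(e) does the same for Course RTX2, and 10.2.8.1 ends the duration of CR at progressive disease.
- The PFS list does not name relapse either. If progression can cover failure after CR there, relapse might cover progression in the EFS list.
- Section 2.4.2 reports an EFS of 81% for the German responders. One relapse alone would leave 31/32 = 96.9% event-free; 81% of 32 implies about 0.19 × 32 = 6 failures, close to the 7 found when progression is counted. Deaths are not given, and this is another study's definition, but it suggests that the EFS cited as background counted progression.

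This makes a drafting omission likely. It does not settle the text. The same sentence in 9.3 uses the two words for two endpoints, 10.2.8.1 also names recurrent and progressive disease as alternatives, and 2.4.2 uses relapse after CR and progressive disease after PR. Two defensible readings give different event counts.

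Other points stand as limits. PFS is reported for the same patients, so a reader would see any gap. Aim 1.2.8 is not without cover, because the RR test picks up early PD. Some progressors may be censored under 8.2(c) rather than remain at risk. The missing start date is minor: 9.3 gives none for OS either, and treatment must start within 5 days (Cohorts A and B) or 14 days (Cohort C) of enrollment.

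**Conclusion.** The EFS definition in 9.3 is wrong as written if taken literally, and ambiguous at best. On the literal reading 2-year EFS can exceed PFS, and the EFS log-rank test in Aim 1.2.8 loses progressions in patients never in CR. On the inclusive reading there is no bias, but no text says that this reading applies.

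The size for this trial cannot be computed. The 0 to 19 point range comes from rituximab responders in another series. Here Cohort A patients in PR go on to LMP-specific T cells, so the range is not an estimate for this study.

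A reader might infer that reported EFS will certainly be inflated, or that progression was left out on purpose. The documents support neither: the first depends on which reading is programmed, and nothing speaks to intent beyond the signs of an omission noted above. Nor does the point reach the primary feasibility endpoint, its power, the futility look or the Bayesian monitoring rules, none of which uses EFS.

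Severity: minor to moderate, confined to secondary Aims 1.2.3 and 1.2.8.

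**What to change.** In 9.3, define EFS as time from the start of protocol therapy (the origin that 10.2.9 gives for PFS) to the first of: progression (PD by 10.2.7) or relapse (recurrence of disease after CR), SMN, or death from any cause. Keep the stated non-events as censoring. Every PFS event is then also an EFS event, so EFS cannot exceed PFS.

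The sponsor should also state how two situations are counted, identically for EFS and PFS: PD at the end of Induction in patients who continue to Arm LMP-TC (4.1.2.2, 4.2.5), and PD not yet confirmed by the repeat scan recommended in 10.2.3. That is a choice about the analysis and leaves treatment unchanged.

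The cost is a line or two of text. No new data are needed, since progression dates are already required for PFS. The downside is that reported EFS may be less favourable and will then differ from PFS mainly by SMN. If the sponsor already meant this definition, only the wording changes.
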